9.2. Effectiveness Assessments

- Objective:
 - 3D Photography
 - Standard 2D Photography
 - Blinded panel assessment on 2D photography
 - Elasticity Measurement
- *Subjective:*
 - S-GAIS
 - P-GAIS
 - SGSQ
 - PGSQ

9.3. Assessment of Safety

Safety assessment will include an evaluation of the treatment area to assess overall quality and integrity of tissue layers for subjects that have completed treatment. All known and unknown events including known risks (see below) will be collected during the conduct of the study regardless of causality.

- Edema
- Infections
- Thermo-injury (i.e. Burns)
- Scarring
- Erythema
- Postoperative pain
- Second-degree burn treatment
- Transient paresthesia

Sensory assessment will be collected using the Numerical Rating Scale (NRS) a 10-point scale to measure pain after treatment.

10. ADVERSE EVENT REPORTING

10.1. Introduction

All observed or volunteered adverse events regardless of treatment group or suspected causal relationship to the ID(s) will be reported as described in the following sections.

For all adverse events, the investigator must pursue and obtain information adequate both to determine the outcome of the adverse event and to assess whether it meets the criteria for classification as a serious adverse event requiring immediate notification to the sponsor or its designated representative. For all adverse events, sufficient information should be obtained by the investigator to try to determine the causality of the event. For adverse events with a suspected causal relationship to the ID, follow-up by the investigator is required until the event or its sequel resolve or stabilize at a level acceptable to the investigator, and Sponsor concurs with that assessment.

10.2. Reporting Period

Serious adverse events require immediate notification within **24 hours** to the Sponsor or its designated representative. When reporting a serious adverse event, the investigator or designee completes the SAE form with as much information as possible however, at a minimum the Subject ID, Name of ID, SAE, and Name of person reporting the event. The completed form must be:

- Emails to the sponsor:

Attention: [name] __ (Vice President Commercialization)

PH: [name]

Email: [contact]

And,

Attention: [name] __ (Study Manager-Thermi Consultant)

[contact]

Email: [contact]

All adverse events (serious and non-serious) must be collected on the subject's CRF from the time the subject signed informed consent through last subject visit.

10.3. Definition of an Adverse Event

An adverse event is any untoward medical occurrence in a clinical investigation associated with the use of an investigational product in human subjects. The event need not necessarily have a suspected causal relationship with the treatment or usage.

Examples of adverse events include but are not limited to:

Investigational Device: ThermiRF

Protocol No.: Thermi_0005

Version Date: Final 10-May-2016

- Abnormal test findings
- Clinically significant symptoms and signs
- Changes in physical examination findings
- Hypersensitivity
- Progression/worsening of underlying disease

Additionally, they may include the signs or symptoms resulting from:

- Product misuse
- Product dependency
- Extravasation
- Study related procedure

10.4. Serious Adverse Events

A medical device adverse event is serious when both of the following criteria are fulfilled:

- The event involves patient/subject/consumer contact
- The event results in:
 - Death
 - Serious deterioration in state of health. This includes:
 - Life-threatening illness or injury
 - Permanent impairment of a body function
 - Permanent damage to a body structure
 - Requires medical or surgical intervention to prevent permanent impairment of a body function or permanent damage to a body structure
 - Requires inpatient hospitalization or prolongation of existing hospitalization

10.5. Severity Assessment

If required on the adverse event case report forms, the investigator will use the adjectives MILD, MODERATE, or SEVERE to describe the maximum intensity of the adverse event. For purposes of consistency, these intensity grades are defined as follows:

MILD	Does not interfere with subject's usual function.
MODERATE	Interferes to some extent with subject's usual function.
SEVERE	Interferes significantly with subject's usual function.

Investigational Device: ThermiRF

Protocol No.: Thermi_0005

Version Date: Final 10-May-2016

Note the distinction between the severity and the seriousness of an adverse event. A severe event is not necessarily a serious event. For example, a headache may be severe (interferes significantly with subject's usual function) but would not be classified as serious unless it met one of the criteria for serious adverse events, listed above.

10.6. Causality Assessment

The investigator's assessment of causality must be provided for all adverse events (serious and non-serious). An investigator's causality assessment is the determination of whether there exists a reasonable possibility that the ID caused or contributed to an adverse event. If the investigator's final determination of causality is unknown and the investigator does not know whether or not ID caused the event, then the event will be handled as "related to ID" for reporting purposes. If the investigator's causality assessment is "unknown but not related to ID", this should be clearly documented on study records.

In addition, if the investigator determines a serious adverse event is associated with study procedures, the investigator must record this suspected causal relationship in the source documents and CRF, as appropriate, and report such an assessment in accordance with the serious adverse event reporting requirements, if applicable.

11. STATISTICAL METHODS AND DETERMINATION OF SAMPLE SIZE

All data collected on CRFs will be presented in data listings. The safety analyses will be carried out using the safety population. All efficacy analyses will be analyzed using the Intent-to-Treat (ITT) population. Any formal statistical tests will be performed at $\alpha = 0.05$ and will be two-sided, unless otherwise specified. All statistical analyses will be conducted in a validated instance of SAS 9.1 or higher. Other analyses, including the creation of figures, may be performed in SAS 9.1 or higher or R 3.2.4 or higher.

11.1. Study Hypothesis

The aim of this study is to evaluate the safety and effectiveness of the ThermiRF™ in the treatment of submental skin laxity with respect to “Lift”. The study design assumes that at least 70% of the population that consists of the target demographic (those that meet the inclusion/exclusion criteria) will have 20 mm² or more of lift. The null hypothesis is that subjects have a response rate of 45% or lower.

11.2. Sample Size Determination

The sample size calculation is based on the following assumptions:

- The true response rate for subjects that do not drop out will be 70%.
- The null response rate is 45%, so a successful trial will reject the null hypothesis that the true response rate is less than or equal to 45%.
- The dropout rate will be approximately 12.5%. While some subjects that drop out may have data from Day 60 that can be carried forward in the primary effectiveness analysis, the sample size calculation assumes that none does and will therefore be treated as non-responders.
- The primary effectiveness analysis is based on a one-sided binomial proportion test that compares the null proportion to the alternative proportion.

Based on these assumptions, a minimum of 68 subjects is required to achieve 80% power at one-sided $\alpha = 0.05$, so a sample size of 70 subjects provides greater than 80% power.

Additionally based on the rule of three, sample size of at least 60 makes it possible to observe any adverse event that occurs with a frequency $> 5\%$ with 95% confidence.

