## 5 SAMPLE SIZE

The null and alternative hypotheses are:

$$\begin{aligned}
 H_0: \pi &\leq 0.45 \text{ (or 45\%)} \text{ vs.} \\
 H_a: \pi &> 0.45
 \end{aligned}$$

where  $\pi$  is the true proportion of subjects with at least 20 mm^2 lift. Under the assumptions that

1.  $\pi = 0.70$  (or 70%) for subjects not prematurely withdrawing from the study; and
2. The dropout rate is 12.5% and all dropouts will be considered as non-responders

a sample of size 70 enrolled subjects provides approximately 85% power to reject the null hypothesis in favor of the alternative at a one-sided  $\alpha=0.05$ .

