### 10.1 PRIMARY EFFECTIVENESS VARIABLE

The primary endpoint is an evaluation of the proportion of subjects with greater than 20 mm^2 lift at Day 90. The following hypothesis will be tested:

$$\begin{aligned} H_0: \pi &\leq 0.45 \text{ (or 45\%)} \\ H_a: \pi &> 0.45 \text{ (or 45\%)} \end{aligned}$$

where  $\pi$  is the proportion of subjects with greater than 20 mm^2 lift at Day 90. Statistical summaries will include the number and percentage of subjects with greater than 20 mm^2 lift at Day 90 and a two-sided 90% confidence interval of the percentage based on the exact binomial distribution. A one-sided exact binomial proportion test will be performed at  $\alpha=0.05$ . For the ITT population, the analysis will be carried out twice as follows:

1. Any subject with missing data at Day 60 and Day 90 will be treated as non-response to the photography (primary analysis). In the case that a subject has a Day 60 image evaluation but is missing the Day 90 image evaluation, the Day 60 evaluation will be carried forward in the primary endpoint analysis.
2. Any subject with missing data at Day 60 and Day 90 will be removed. In the case that a subject has a Day 60 image evaluation but is missing the Day 90 image evaluation, the Day 60 evaluation will be carried forward in the primary endpoint analysis.

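### Does the Protocol's minimum of 68 subjects for 80% power, which its stated inputs do not reproduce exactly, need correcting?

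*Protocol*

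**What the plan says.** Protocol section 11.2 lists its inputs. On response: "The true response rate for subjects that do not drop out will be 70" per cent. On the null: "The null response rate is 45%, so a successful trial will reject the null hypothesis". On dropout: "The dropout rate will be approximately 12.5" per cent, with every dropout counted as a non-responder for sizing purposes. The test is a one-sided binomial proportion test at 0.05. From these it concludes that "a minimum of 68 subjects is required to achieve 80% power", and continues: "so a sample size of 70 subjects provides greater than 80% power".

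SAP section 5 uses the same hypotheses and the same 70% response. It states the dropout rate without a qualifier: "The dropout rate is 12.5% and all dropouts will be considered as non-responders". It does not repeat the 68 and reports only the power at the planned size: "a sample of size 70 enrolled subjects provides approximately 85% power to reject the null hypothesis". SAP section 10.1 settles which binomial test is meant: "A one-sided exact binomial proportion test will be performed at" the 0.05 level.

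**The concern.** A sample-size paragraph should be reproducible from the inputs printed in it, and this one is not. At exactly 12.5% dropout, sizes below 68 already deliver 80% power, and 68 itself delivers almost 85%.

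The two documents also sit oddly together. The Protocol ties 80% to 68 subjects and the SAP ties about 85% to 70, as though two more subjects bought five points of power. A reader could suspect that the two calculations used different methods or dropout rates, or that dropout was counted twice. If the error ran the other way, or reached the planned size, the trial could be underpowered for its only formally sized hypothesis. So the figure is worth checking.

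**Working it through.** **Inputs.** Null p0 = 0.45, response in non-dropouts 0.70, dropout 0.125 with dropouts kept in the denominator as failures, one-sided α = 0.05 (Protocol section 11.2, SAP section 5); exact binomial test (SAP section 10.1). Effective alternative: p1 = 0.70 × (1 − 0.125) = 0.6125.

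**Method.** For each n, the critical value r is the smallest count with P(X ≥ r | n, 0.45) ≤ 0.05. Power is P(X ≥ r | n, 0.6125).

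| n | r | attained α | power |
|---|---|---|---|
| 60 | 34 | 0.046 | 80.6% |
| 61 | 35 | 0.035 | 77.5% |
| 62 | 35 | 0.046 | 81.8% |
| 63 | 36 | 0.035 | 78.9% |
| 64 | 36 | 0.047 | 82.9% |
| 65 | 37 | 0.036 | 80.1% |
| 66 | 37 | 0.047 | 83.9% |
| 67 | 38 | 0.036 | 81.3% |
| 68 | 38 | 0.047 | 84.9% |
| 69 | 39 | 0.036 | 82.4% |
| 70 | 39 | 0.047 | 85.8% |

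**The figures for the planned size.** At 70 the exact power is 85.8%. That is more than 80%, as the Protocol says, and about 85%, as the SAP says. Seventy is also the first n at which exact power reaches 85%.

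**The 68.** Exact power is saw-toothed because r moves in whole numbers. The first n reaching 80% is 60, and the smallest n from which every larger n also reaches 80% is 64. The one-sample normal approximation gives

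n = [(1.645 × √(0.45 × 0.55) + 0.842 × √(0.6125 × 0.3875)) / (0.6125 − 0.45)]² = 57.1, so 58,

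or 63.1, so 64, with a continuity correction. None of these is 68.

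**Sensitivity to the dropout rate.** The same exact calculation with p1 = 0.70 × (1 − d):

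| dropout d | first n at 80% | 80% held from | power at n = 70 |
|---|---|---|---|
| 12.0% | 58 | 62 | 87.1% |
| 12.5% | 60 | 64 | 85.8% |
| 12.8% | 62 | 66 | 85.0% |
| 12.9% | 62 | 68 | 84.7% |
| 13.0% | 62 | 68 | 84.4% |
| 13.2% | 64 | 68 | 83.8% |
| 13.5% | 66 | 70 | 82.9% |
| 14.0% | 68 | 74 | 81.3% |
| 15.0% | 76 | 82 | 77.9% |

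A rate of 12.9%, which is 0.4 points above the printed figure, gives a sustained minimum of exactly 68 and a power of 84.7% at 70, which also rounds to the SAP's figure. Other routes end near 68. Rounding the number of dropouts up to a whole subject gives a sustained minimum of 66. Inflating for dropout a second time gives 60 × 1.125 = 67.5 or 59 / 0.875 = 67.4, both 68 when rounded up. The documents do not say which route, if any, was taken.

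**The case for a change.** The strongest case for a correction is that the Protocol presents 68 as following from the assumptions it lists, and the rate it prints is 12.5%. At that rate no standard one-sided calculation gives 68. Reaching it takes a different dropout rate or a double allowance for dropout, and neither is disclosed. Replacing the sentence would take one line, and it could add something useful: 70 subjects keep 80% power only up to about 14.4% dropout.

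The arithmetic in that case stands: 68 is not reproduced at exactly 12.5%, and its derivation is missing. Three parts of it carry less weight.

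- The Protocol qualifies the rate as approximate. The SAP's unqualified 12.5% does not remove that qualifier, because the SAP was prepared from the Protocol and cannot show what input the earlier calculation used.
- The size of the discrepancy depends on a convention that neither document states. It is 68 − 60 = 8 against the first n reaching 80%, and 68 − 64 = 4 against the sustained n.
- A statement of how much dropout the design tolerates would be welcome, but its absence is not an error, since neither document undertakes to give one.

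Nor is the change quite free. Under Protocol section 13.1, even an administrative change needs the sponsor's agreement and written notification to the ethics board.

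**Conclusion.** No change is needed. The 68 is an intermediate figure with an undocumented derivation, and it falls within reach of small rounding in an input given only approximately. It errs on the safe side: under the stated assumptions 68 subjects give 84.9% power, more than the 80% claimed.

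Nothing in the trial depends on it. Enrolment is 70, the exact test rejects at 39 or more responders of 70 with attained α of 0.047, and both power statements for 70 hold. Explaining or deleting 68 would alter none of these, nor any conclusion the trial can reach.

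This rests on the documents' own planning values: 70% response in non-dropouts, dropout near 12.5% all counted as failure, and the exact one-sided test. If dropout rose beyond about 14.4%, power at 70 would fall below 80% (77.9% at 15%). That is a feature of the chosen design, and correcting the 68 would not change it.

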11.3. Analysis Populations

- **Intent-to-Treat (ITT):** The ITT population includes all subjects that meet inclusion/exclusion criteria, have a signed informed consent form, and are enrolled in the study. The primary effectiveness analysis will be on the ITT population.
- **Safety:** The safety population will include all randomized subjects who received at least one treatment.

Investigational Device: ThermiRF

Protocol No.: Thermi_0005

Version Date: Final 10-May-2016

- **Per-Protocol Population (PPP):** The PPP will include all subjects who:

- Completed the Day 90 visit
- Have an evaluable photograph to estimate area of lift from the Day 90 visit
- Have not used an excluded medication

11.4. Demographics and Baseline Characteristics

Demographic data and baseline characteristics will be summarized for the Safety population. Demographic data (age, gender, ethnicity and race) and baseline characteristics (height, weight, BMI, heart rate, respiration, blood pressure, and temperature) will be summarized in a table and presented in a listing. A summary of all prior and concomitant medications will be presented.

11.5. Analyses

11.5.1 Primary Effectiveness Analysis

The primary effectiveness analysis will compare the proportion of subjects who respond to treatment by achieving at least 20 mm² of lift of the submental region to a null proportion 45% using a one-sided binomial proportion test at $\alpha = 0.05$. Responders will be determined based on change from baseline of area as measured by Vectra XT 3D photography in standard lighting conditions. The primary effectiveness analysis will be based on the ITT population, so any missing data, including withdrawn consent and lost to follow up, will be treated as non-response.

11.5.2 Secondary Effectiveness Analyses

Analysis of all effectiveness endpoints will be conducted on the ITT population and on the PP population. Continuous endpoints will be tested using the paired *t*-test, ordinal endpoints will use the Wilcoxon-Pratt signed rank test, and binary endpoints will be tested using the binomial proportion test.

Raters' assessment of improvement will be validated based on a comparison of the blinded raters' assessments to unblinded raters' assessments at Day 60 as outlined in Kim et al. (Kim et al. 2004) using 30 subjects at Day 60 selected at random. Two unblinded clinicians, who know which photos are baseline and which are Day 60, will assess the 2D photography at baseline and Day 60. Three blinded clinicians, who do not know which photos are baseline and which are Day 60, will assess the same photos. The assessments of the unblinded and blinded raters will be compared using Cohen's unweighted kappa statistic (Fleiss et al. 1969). The assessments will be considered validated according to the scale detailed by Landis et al. (Landis & Koch 1977), where <0.00 is considered poor agreement, 0.00-0.20 is slight agreement, 0.21-0.40 is fair agreement, 0.41-0.60 is moderate agreement, 0.61-0.80 is substantial agreement, and >0.80 is almost perfect agreement. Accordingly, any score greater than 0.60 will validate the method.

11.5.3 Interim Analysis

N/A

11.5.4 Safety Analysis

All safety analyses and summaries will be based on the Safety population. The number and percentage of subjects reporting AEs during the study will be tabulated by MedDRA system organ class (SOC) and preferred term within each SOC. SOCs will be listed in order of descending frequency. Preferred terms will be listed in order of descending frequency within each SOC. Summaries and listings will be provided for subjects reporting SAEs, subjects experiencing AEs related to study medication and subjects withdrawing due to an AE.

Subjects experiencing serious adverse events, treatment-related adverse events and discontinuation from the study due to adverse events will also be summarized.

Treatment-related adverse events will include events marked as being at least possibly or probably related to the study treatment. Adverse events will be presented by severity and by relation to treatment.

Subject disposition at Visit 1 will be presented. Enrollment status with respect to number of subjects enrolled, completed, lost-to-follow and discontinuation regardless of reason will be presented.

Concomitant medications will be summarized.

11.6. Statistical Analysis Plan

A separate statistical analysis plan (SAP) will contain all details needed to carry out the statistical analysis, including specific statistical tests for all effectiveness endpoints, adjustments for multiple testing, specific derivations, and specifications for the tables, listings, and figures.

Investigational Device: ThermiRF

Protocol No.: Thermi_0005

Version Date: Final 10-May-2016

12. QUALITY CONTROL AND QUALITY ASSURANCE

During study conduct, the sponsor or its agent will conduct periodic monitoring reviews (in person or remote) to oversee the progress of the clinical trial and to ensure that it is conducted, recorded, and reported in accordance with the protocol, Standard Operating Procedures (SOPs) as applicable, Good Clinical Practice (GCP), and the applicable regulatory requirement(s).

The sponsor representative may review source documents to confirm that the data recorded on CRFs/eCRF is accurate. The investigator and institution will allow Sponsor's representative or its agents, and appropriate regulatory authorities, direct access to source documents to perform this verification.

The study site may be subject to review by the institutional review board (IRB)/independent ethics committee (IEC), and/or to quality assurance audits performed by Sponsor, and/or to inspection by appropriate regulatory authorities.

It is important that the investigator(s) and their relevant personnel are available during any in-person monitoring visits and possible audits or inspections, and that sufficient time is devoted to the process.

13. ADMINISTRATIVE REQUIREMENTS

13.1. Protocol Amendments and Administrative Changes

Amendments and administrative changes are not to be made to this protocol without consultation with and the agreement of the Sponsor. The investigator and Sponsor should discuss amendment or administrative change. If agreement is reached, such amendment or administrative change will be developed in writing by the Sponsor and submitted to the investigator.

The investigator will be responsible for ensuring that all protocol amendments are approved in writing by the appropriate IRB or IEC before the institution of the changes specified in the amendment (except when necessary to eliminate an immediate hazard to the subjects). The investigator will also ensure that the Sponsor receives a copy of the written IRB or IEC approval of these changes.

The investigator will be responsible for ensuring that the IRB or IEC receives written notification of all administrative changes to the protocol prior to institution of the specified changes. The investigator will ensure that the Sponsor receives a copy of these written notifications.

13.2. Data Handling and Record Keeping

The investigator will document all study related procedures directly on the source record or medical chart as the primary source of data collection. Study related information/data points required by the sponsor for analysis will be transcribed by the investigator or designee from the source record, onto the CRF/eCRF (data collection tool) for this study using good documentation practices.

In some instances, the sponsor will provide a CRF template for use as the primary source of data collection.

The investigator is encouraged, however not required to maintain additional source records on matters respective to the subject's safety and wellbeing not already captured on the CRFs/eCRF or source template.

Black or blue ink must be used on all data collection requirements. All errors and omissions must be crossed out by means of a single line, and the date and initials of the correction or addition of correct information must be provided. Use of white-out or write-overs will not be permitted. All study related records will be kept in a secure and locked location, and shall only be accessible to the assigned study personnel during the conduct of the study, and to the regulatory authorities in the event of an inspection.

